6.1.3. Subgroup Analysis of the Primary Efficacy Endpoint

Point estimates and 95% exact confidence intervals (CIs) of the SVR12 rates based on Clopper-Pearson method will be displayed {20839} on FAS by randomized treatment and FAS by actual treatment for each subgroup. Subgroups are outlined in Section 3.4. Subgroup factors used for randomization will be summarized separately.

SVR12 rates will be summarized by categories of early viral response to explore possible early on-treatment predictors of SVR12. The relationship between SVR12 and study drug dose reduction and modification are also explored.

Forest plot of SVR12 by Subgroup and treatment groups for each cohort will be provided. No statistical comparisons are performed for the subgroup analyses.

6.2. Secondary Efficacy Endpoints

6.2.1. Definition of Secondary Efficacy Endpoints

The following secondary antiviral efficacy endpoints will be analyzed:

- The proportion of subjects with HCV RNA < LLOQ (ie, < 15 IU/mL) at 4, 12 and 24 weeks after discontinuation of therapy (SVR 4, SVR12 and SVR 24)
- The proportion of subjects with HCV RNA below LLOQ (ie, < 15 IU/mL) by study visit
- HCV RNA (\log_{10} IU/mL) and change from baseline in HCV RNA (\log_{10} IU/mL) through end of treatment
- The proportion of subjects with virologic failure as the following:

On-treatment virologic failure

- HCV RNA \geq LLOQ after having previously had HCV RNA < LLOQ, while on treatment, confirmed with 2 consecutive values (note, second confirmation value can be posttreatment), or last available on-treatment measurement with no subsequent follow up values (ie, breakthrough)
- $> 1 \log_{10}$ IU/mL increase in HCV RNA from nadir while on treatment, confirmed with 2 consecutive values (note, second confirmation value can be posttreatment), or last available on-treatment measurement with no subsequent follow up values (ie, rebound)
- HCV RNA persistently \geq LLOQ through 8 weeks of treatment (ie nonresponse)

Relapse

- HCV RNA \geq LLOQ during the posttreatment period having achieved HCV RNA < LLOQ at end of treatment, confirmed with 2 consecutive values or last available posttreatment measurement

6.2.2. Analysis Methods for Secondary Antiviral Efficacy Endpoints

The point estimates of SVR4, SVR12, SVR24 rates and their 2-sided 95% exact confidence intervals (CIs) based on Clopper-Pearson method will be provided as applicable {[Clopper 1934](#)}, on FAS by randomized treatment and FAS by actual treatment.

For analyses of HCV RNA < LLOQ (ie, < 15 IU/mL) by visit while on treatment and during the posttreatment (SVR) follow-up period, subjects will be assigned a value at each visit based on the categorical imputation rules described in Section 3.6. The 2-sided 95% exact confidence interval based on Clopper-Pearson method will be provided for the proportion. The overall category for “HCV RNA < LLOQ” will be split into the following 2 subcategories: “< LLOQ

TND" for subjects with target not detected and "< LLOQ detected" for subjects with < LLOQ in tabular displays.

Graphs for the proportion of subjects with HCV RNA < LLOQ over time on treatment and during the posttreatment follow-up period will be displayed.

[figure not shown]
Summary statistics will be presented for absolute values and change from baseline in HCV RNA (\log_{10} IU/mL) by visit through end of treatment (EOT). Imputation rules described in Section 3.6 will be used to assign HCV RNA values for missing values at a visit that are bracketed by "< LLOQ TND" and/or "< LLOQ detected". Otherwise, a missing = excluded analysis will be performed. Plots of the mean \pm SD and median (Q1, Q3) of absolute values and changes from baseline in HCV RNA through end of treatment will be presented.

For the SVR12 endpoint analysis, a summary table of the number and percentage of subjects with SVR12, virologic failure (VF), and Other will be created. All subjects who achieve SVR12 will be categorized as SVR12. Virologic failure will be descriptively summarized as "on-treatment virologic failure" and relapse (which will be broken down by study drug completed yes/no). Subjects who do not achieve SVR12 and do not meet criteria for VF will be categorized as "Other". The denominator for relapse will be the number of subjects who had HCV RNA < LLOQ on their last observed on-treatment HCV RNA measurement; otherwise, the denominator will be the number of subjects in FAS by randomized treatment or FAS by actual treatment, depending on the analyses population used.

A concordance table between SVR12 and SVR24 will be provided by treatment group for each cohort and overall. Subjects with both observed SVR12 and observed SVR24 data will be included for this analysis.

6.3. Exploratory Efficacy Endpoints

6.3.1. Definition of Exploratory Efficacy Endpoints

6.3.2. Analysis Methods for Exploratory Efficacy Endpoints

PPD

6.4.2. Change on Sample Size

The initial sample size planned was 430, with 90 each in groups 1 and 2, and 125 each in group 3 and 4 to obtain a 10% non-inferiority margin at 1-sided 0.025 level and 90% power, for the comparisons between group 1 and 2, and between group 3 and 4.

Due to lack of feasibility of enrolling subjects, the study was early terminated after 87 subjects enrolled, with 17, 17, 26, 27 randomized in groups 1-4 respectively. Five subjects randomized were never dosed so final analyses set has only 82 subjects (15, 17, 26, 24 for randomization groups 1-4 respectively, while 16, 17, 25, 24 for actual treatment groups 1-4 respectively). Details for subjects with different treatment groups in the two FAS populations are specified in Section 6.4.1.

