3.1.2. Full Analysis Set

The Full Analysis Set (FAS) includes all enrolled subjects who took at least 1 dose of study drug. The study drugs in this study are LDV/SOF FDC, with or without RBV. The difference between the FAS definition provided in the protocol and this SAP is documented in Section [6.4](#).

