3.1.2.2. Full Analysis Set by Actual Treatment

Subjects are grouped according to their cirrhotic status and the treatment/duration they actually received. This is applied for key efficacy analyses.

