3.6.1. Missing Data

For missing last dosing date of study drug, imputation rules are described in Section 3.8.1. The handling of missing or incomplete dates for adverse event (AE) onset is described in Section 7.1.5.2, and for prior and concomitant medications in Section 7.4.

For analyses of categorical HCV RNA data, missing posttreatment HCV RNA data will have the missing data imputed. Missing on-treatment HCV RNA will have missing data imputed up to the time of the last dose (for on-treatment displays). If the study day associated with the last dosing date of any study drug is greater than or equal to the lower bound of a visit window, and the value at the visit is missing, then the value will be imputed. If the study day associated with the last dosing date is less than the lower bound of a visit window then the on-treatment value at that visit will remain missing.

If an HCV RNA data point is missing and is preceded and followed in time by values that are “< LLOQ target not detected (TND),” then the missing data point will be set to “< LLOQ TND.”

If a data point is missing and preceded and followed by values that are “< LLOQ detected,” or preceded by “< LLOQ detected” and followed by “< LLOQ TND,” or preceded by “< LLOQ TND” and followed by “< LLOQ detected,” then the missing value will be set to “< LLOQ detected.” In these situations the data point will be termed a bracketed success; otherwise, the data point will be termed a bracketed failure (ie, \geq LLOQ detected). If a data point is missing and is not bracketed, the missing data point will also be termed a failure (ie, \geq LLOQ detected) except for SVR24, which will be imputed according to SVR12 status. Success for SVR12 who have no further HCV RNA measurements collected will be counted as a success for SVR24 due to the high correlation between these 2 endpoints.

For the analyses of continuous HCV RNA efficacy data, when a missing HCV RNA value is imputed as < LLOQ TND or < LLOQ detected according to the imputation rule described above, the corresponding continuous value will be imputed to LLOQ – 1 IU/mL. No other imputation will be performed for continuous HCV RNA data.

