6. EFFICACY ANALYSES

All the efficacy analyses are conducted on FAS by randomized treatment and on FAS by actual treatment, unless specified otherwise.

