6.1. Primary Efficacy Endpoint

6.1.1. Definition of the Primary Efficacy Endpoint

The primary efficacy endpoint is SVR12 defined as HCV RNA < LLOQ (ie, < 15 IU/mL) 12 weeks after discontinuation of the study drug in the FAS. The COBAS® AmpliPrep/COBAS® TaqMan® HCV Quantitative Test, version 2.0 will be used to measure HCV RNA. HCV genotype and subtype will be determined using the Siemens VERSANT® HCV Genotype INNO-LiPA 2.0 Assay, or other alternative assay decided by Gilead.

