6.1.2. Summary for the Primary Efficacy Endpoint

The primary efficacy endpoint is SVR12 (HCV RNA < LLOQ 12 weeks after discontinuation of therapy). The primary analysis will be performed after all enrolled subjects have been followed through 12 weeks posttreatment or discontinued from study.

In the primary efficacy analysis, the SVR12 rate will be summarized by FAS by randomized treatment and by FAS by actual treatment, the 2-sided 95% exact CI of SVR12 based on Clopper-Pearson method will be provided {[Clopper 1934](#)}.

In Cohort 1, a non-inferiority test of SVR12 rates will be performed comparing Group 1 and 2. A non-inferiority margin of 10% will be applied. Non-inferiority will be established if the lower bound of the 2-sided 95% confidence interval (CI) of the difference in SVR12 (Group 1 - Group 2) is greater than -10%. The CI will be constructed using stratum-adjusted Mantel-Haenszel (MH) proportions, stratified by the randomization stratification factors (i.e., genotype 1 or 4; prior SOF therapy in combination with SMV or without SMV).

A similar non-inferiority tests of SVR12 rates will be performed comparing Group 3 and 4 in Cohort 2. The NI margin of 10% is chosen primarily based on clinical judgment. The statistical justification of a NI margin is based on a two-step process in which: 1) we estimate the treatment benefit of the control regimens (LDV/SOF + RBV for 12 weeks for cohort 1; LDV/SOF for 24 weeks for cohort 2) and the historical control (M1), and 2) we define a margin which preserve some fraction of the treatment benefit characterized in Step 1 above (M2).

The M1 and M2 in the current study design as follows:

- M1 = the smallest treatment benefit of the control regimens over the historical control
- M2 = 50% of M1

Based on the Phase 2 ELECTRON-2, GS-US-337-1118, and SYNERGY data, the SVR12 rates for LDV/SOF + RBV for 12 weeks are summarized below:

Table 6-1. Summary of SVR12 Rates in Phase 2 Studies

Study	SVR12 Rates			
	LDV/SOF 12 Weeks		LDV/SOF + RBV 12 Weeks	
Electron-2			n/a	Without cirrhosis: 100% (19/19)
GS-US-337-1118			With cirrhosis: 100% (14/14)	Without cirrhosis: 100% (36/36)
SYNERGY	Advanced liver disease (Knodell score 3, 4) 100% (7/7)	Other (Knodell score 0, 1) 100% (7/7)		
Overall	100% (7/7) 95% CI: (59%, 100%)	100% (7/7) 95% CI: (59%, 100%)	100% (14/14) 95% CI: (77%, 100%)	100% (55/55) 95% CI: (94%, 100%)

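### Does analysing SVR12 on two Full Analysis Sets that both leave out the same five never-dosed subjects leave a gap in the plan?

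*SAP*

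**What the plan says.** Section 6.4.2 gives the enrolment at early termination as 87 subjects, "with 17, 17, 26, 27 randomized in groups 1-4 respectively", and accounts for the loss to 82: "Five subjects randomized were never dosed so final analyses set has only 82 subjects". The FAS then holds 15, 17, 26 and 24 subjects by randomised group, or 16, 17, 25 and 24 by actual group.

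Section 3.1.2 sets one entry rule: "The Full Analysis Set (FAS) includes all enrolled subjects who took at least 1 dose of study drug". Two groupings of that set follow. Section 3.1.2.1 groups by randomised treatment and makes this the primary efficacy set. Section 3.1.2.2 regroups the same people: "Subjects are grouped according to their cirrhotic status and the treatment/duration they actually received". Section 3.2 gives the reason for having both, namely that randomisation errors may have put cirrhotic subjects in Cohort 1 and non-cirrhotic subjects in Cohort 2.

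Section 6 applies both versions throughout ("All the efficacy analyses are conducted on FAS by randomized treatment and on FAS by actual treatment, unless specified otherwise"), and Section 6.1.2 repeats this for the primary endpoint ("the SVR12 rate will be summarized by FAS by randomized treatment and by FAS by actual treatment"). Section 6.1.1 defines SVR12 as HCV RNA below the quantitation limit "12 weeks after discontinuation of the study drug in the FAS". Sections 3.5, 6.1.2 and 6.4.3 call the non-inferiority comparisons exploratory, and the last two add that the sample is too small to power them.

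**The concern.** Two analysis sets for one endpoint suggest a robustness check. Here both sets hold the same 82 people, so agreement between them is no evidence about the five who were left out. All five had been randomised to the arms without ribavirin (Groups 1 and 4), in an open-label trial where subjects knew their assignment. Subjects who withdraw once they know their arm can bias a comparison.

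With arms of 15 to 26 subjects, two or three people matter against a 10-point margin. The losses also fall on opposite sides: in the test arm (Group 1) in Cohort 1 and in the control arm (Group 4) in Cohort 2. Appendix 1 lists no SVR12 table on all 87 subjects. A reader could conclude that the plan hides how much the exclusion moves the result, and that an as-randomised table with the five scored both ways is missing.

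**Working it through.** **1. The plan's own counts (Section 6.4.2).**
- Randomised: 17 + 17 + 26 + 27 = 87.
- FAS by randomised treatment: 15 + 17 + 26 + 24 = 82. FAS by actual treatment: 16 + 17 + 25 + 24 = 82.
- Never dosed: 87 - 82 = 5, as stated. By group: 17 - 15 = 2, 17 - 17 = 0, 26 - 26 = 0, 27 - 24 = 3.
- Actual minus randomised: +1, 0, -1, 0, a net move of one subject from Group 3 to Group 1. This is the kind of misplacement that Section 3.2 describes.

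The figures agree, and the two versions do omit the same five subjects.

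**2. Is the imbalance evidence of bias?** Fisher's exact test, two-sided, gives p = 0.48 for 2/17 v 0/17 and p = 0.24 for 3/27 v 0/26. Pooling the two arms without ribavirin against the two with it (5/44 v 0/43) gives p = 0.055, but that grouping was chosen after seeing the pattern and crosses the cohorts that the plan compares separately. Bias is possible and not shown.

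**3. Shift in the crude difference.** Let r be a common SVR12 rate in dosed subjects, assumed to lie between 0.90 and 1.00 (the SAP gives no results).
- Never-dosed as failures. Cohort 1: -r × 2/17, from -10.6 to -11.8 points. Cohort 2: +r × 3/27, from +10.0 to +11.1.
- Never-dosed as successes. Cohort 1: (1 - r) × 2/17, from +1.2 to 0.0. Cohort 2: -(1 - r) × 3/27, from -1.1 to 0.0.

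**4. Lower 95% limits against the -10% margin.** Stratum counts are not given, so these are unstratified Newcombe limits rather than the SAP's Mantel-Haenszel interval: L = d - √[(p1 - l1)² + (u2 - p2)²], where d = p1 - p2 and l, u are Wilson limits. For example, with 26/26 v 24/24, l1 = 26/(26 + 1.96²) = 0.871 and u2 = 1, so L = -(1 - 0.871) = -12.9%.

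| Assumed dosed failures (test, control) | FAS | Never-dosed as failures | Never-dosed as successes |
|---|---|---|---|
| Cohort 1: 0, 0 | -20.4 | -34.3 | -18.4 |
| Cohort 1: 1, 0 | -29.8 | -41.0 | -27.0 |
| Cohort 1: 0, 1 | -15.1 | -29.0 | -13.2 |
| Cohort 1: 1, 1 | -24.4 | -35.6 | -21.6 |
| Cohort 2: 0, 0 | -12.9 | -3.7 | -12.9 |
| Cohort 2: 1, 0 | -18.9 | -9.4 | -18.9 |
| Cohort 2: 0, 1 | -9.2 | -0.8 | -9.5 |
| Cohort 2: 1, 1 | -15.1 | -6.5 | -15.5 |

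In Cohort 1 neither scoring crosses the margin. In Cohort 2 the success scoring stays on the same side as the FAS in every row. Only the failure scoring crosses, and it does so towards non-inferiority, because it charges the control regimen with three people who never took it.

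**5. Does either scoring have a basis in the SAP?** Section 6.1.1 times SVR12 from stopping study drug, so a subject who never started has no time point. Section 3.6.1 does say "If a data point is missing and is not bracketed, the missing data point will also be termed a failure", but that rule covers missing HCV RNA values at visits of treated subjects. For the success scoring, Section 6.1.2 takes 5% as the highest spontaneous SVR12 rate. Three successes out of three untreated subjects would then have probability at most 0.05³ = 0.000125, assuming independence.

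**6. What the tests can bear.** Normal-approximation power is Φ(0.10/√[p(1 - p)(1/n1 + 1/n2)] - 1.96). With the planning rates of 98% and 95% it is 52% at 15 v 17 and 37% at 26 v 24. Restoring all five subjects gives 55% at 17 v 17 and 39% at 26 v 27. The tests are weak with or without them.

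**The case for a change.** The best case for the concern is that an as-randomised analysis is the customary companion to one restricted to dosed subjects. Here the losses are one-sided, the arms are small, and the shift under one scoring exceeds the margin. The two scorings together would bracket the effect at the cost of one table. A reader who adds the five back as failures, by analogy with the rule in Section 3.6.1, would get a flattering answer in Cohort 2 with nothing beside it to warn that the scoring produced it.

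The facts in that case stand: the counts are right, the two versions cannot reveal the effect of the exclusion, and Appendix 1 has no efficacy output on all randomised subjects. They do not amount to a fault. The SAP does not claim that the second version tests the exclusion. The success scoring nearly repeats the FAS result, and the failure scoring in Cohort 2 would put a misleading row into the report. Nor is the exclusion hidden: Section 4.1 tabulates the never-treated by group, listing 16.2.3 shows who was excluded, and table 15.9.1.1 gives SVR12 on the primary set. Adding 2 or 3 to a denominator recovers the crude differences, and only the interval is not supplied.

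A related wording conflict is real. Section 3.1.1 groups the all-randomised set by treatment received, while Section 3.2 groups it by randomised treatment. It touches no planned efficacy table. Section 3.2 also lets actual treatment default to the randomised one unless a different treatment was taken for the whole duration. It is clerical.

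**Conclusion.** The concern does not hold. The two FAS versions omit the same five subjects, as the counts show, but the plan uses the second version to handle misplacement between cohorts and treatments, and it does that. Requiring a dose is stated openly and fits an endpoint timed from the end of dosing.

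What remains is a wish for an additional post hoc table, on which statisticians may reasonably differ. It would move the crude difference by 10 to 12 points under one convention and by about 1 point or less under the other, and it would change no conclusion, since the tests are exploratory and have roughly 37% to 52% power.

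These sizes assume 90% to 100% SVR12 in dosed subjects, or at most one dosed failure per arm for the limits, and unstratified intervals. Section 6.4.1, which the contents list names as covering the change to the FAS, was not available for this review. It may give the reasons for non-dosing, and the conclusion does not depend on it.

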6.4.3. Non-inferiority Comparisons

Although the non-inferiority comparisons of SVR12 in the non-cirrhotic cohort (group 1 vs. 2) and in the compensated cirrhotic cohort (group 3 vs. 4) were performed, the results are for exploratory purpose only and the interpretation needs to be cautious since the actual sample size does not have enough power for the test.

7. SAFETY ANALYSES

All the safety analyses are conducted on Safety Analysis Set, unless specified otherwise.

7.1. Adverse Events and Deaths

7.1.1. Adverse Event Dictionary

Clinical and laboratory AEs will be coded using the most recent available MedDRA code. System organ class (SOC), high level group term (HLGT), high level term (HLT), preferred term (PT), and lower level term (LLT) will be provided in the AE dataset.

7.1.2. Adverse Event Severity

Adverse events are graded by the investigator as Grade 1, 2, 3, or 4 according to toxicity criteria specified in the protocol. The severity grade of events for which the investigator did not record severity will be categorized as “missing” for tabular summaries and data listings, and the most severe will be considered (for sorting purpose only) in data presentation.

7.1.3. Relationship of Adverse Events to Study Drug

Related AEs are those for which the investigator selected “Related” on the AE case report form (CRF) to the question of “Related to Study Treatment.” Events for which the investigator did not record the relationship to study drug will be considered to be related to study drug for summary purposes. However, by-subject data listings will show the relationship as missing from that captured on the CRF.

7.1.4. Serious Adverse Events

Serious adverse events (SAEs) will be identified and captured as SAEs if AEs met the definitions of SAE specified in the study protocol. Serious adverse events captured and stored in the clinical database will be reconciled with the SAE database from the Gilead Drug Safety and Public Health Department before database finalization.

7.1.5. Treatment-Emergent Adverse Events

7.1.5.1. Definition of Treatment-Emergent

Treatment-emergent adverse events (TEAEs) are defined as one or both of the following:

- Any AEs with an onset date on or after the study drug start date and no later than 30 days after permanent discontinuation of study drug
- Any AEs leading to premature discontinuation of study drug.

7.1.5.2. Incomplete Dates

If the onset date of AE is incomplete, then the month and year (or year alone if month is not recorded) of onset determine whether an AE is treatment emergent, as long as the AE stop date is not prior to the first dose date of study drug. The event is considered treatment emergent if both of the following 2 criteria are met:

- The AE onset and end dates are the same as or after the month and year (or year) of the first dose date of study drug
- The AE onset date is the same as or before the month and year (or year) of 30th day after the date of the last dose of study drug

An AE with a completely missing onset and stop dates, or with the onset date missing and a stop date later than the first dose date of study drug, will be considered to be treatment-emergent.

7.1.6. Summaries of Adverse Events and Deaths

A brief high-level summary of TEAEs will be provided by treatment group for each cohort and overall and by the number and percentage of subjects who had the following: any AE, any AE of Grade 3 or above, any treatment-related AE, any treatment-related AE of Grade 3 or above, any SAE, any treatment-related SAE, any AE that led to premature discontinuation of any study drug, any AE that led to premature discontinuation of LDV/SOF, any AE that led to premature discontinuation of RBV, any AE that led to modification or interruption of any study drug, any AE that led to interruption of LDV/SOF, any AE that led to modification or interruption of RBV. All deaths (including those that are treatment emergent and those that are not treatment emergent) observed during the study will also be summarized and included in this table.

Adverse event summaries will provide the number and percentage of subjects with TEAEs by SOC and PT, by treatment group in each cohort on the Safety Analysis Set as follows:

- All AEs
- AEs of Grade 3 or above
- All treatment-related AEs
- Treatment-related AEs of Grade 3 or above
- All SAEs
- All treatment-related SAEs
- AEs leading to premature discontinuation of any study drug
- Adverse Events Leading to Modification or Interruption of Any Study Drug

Multiple events will be counted once only per subject in each summary. Adverse events will be summarized and listed first in alphabetic order of SOC and then by PT in order of descending incidence of the overall treatment group within each SOC. In summaries by severity grade, the most severe grade will be used for those AEs that occurred more than once in an individual subject during the study.

In addition to the above summary tables, TEAEs will also be summarized by PT only, in order of descending incidence within the overall treatment group for:

- AEs that occurred in at least 5% of subjects within any treatment group
- AEs of Grade 3 or above
- All treatment-related AEs
- All SAEs
- AEs leading to premature discontinuation of any study drug
- AEs leading to premature discontinuation of LDV/SOF
- AEs leading to premature discontinuation of RBV (groups 2 and 3 only)
- AEs leading to premature discontinuation of all study drugs
- AEs leading to modification or interruption of any study drug
- AEs leading to modification or interruption of RBV (groups 2 and 3 only)

In addition to the by-treatment summaries described above, data listings will be provided for the following:

- All AEs
- AEs of Grade 3 or above
- SAEs
- Deaths
- AEs leading to premature discontinuation of any study drug
- Adverse Events Leading to Modification or Interruption of Any Study Drug

7.2. **Laboratory Evaluations**

Laboratory data collected during the study will be analyzed and summarized using both quantitative and qualitative methods. Summaries of laboratory data will be provided for the Safety Analysis Set and will include data collected up to last dose of any study drug plus 30 days for subjects who have permanently discontinued study drug. The analysis will be based on values reported in conventional units. When values are below the limit of quantitation, they will be listed as such, and the closest imputed value will be used for the purpose of calculating summary statistics. For example, if “< 0.2” was recorded, a value of 0.1 will be used for the purpose of calculating summary statistics; if “< 0.1” was recorded, a value of 0.09 will be used for the purpose of calculating summary statistics.

A by-subject listing for laboratory test results will be provided by subject ID number and visit in chronological order for hematology, serum chemistry, and urinalysis separately. Values falling outside of the relevant reference range and/or having a severity grade of 1 or higher on the Gilead Grading Scale for Severity of Adverse Events and Laboratory Abnormalities will be flagged in the data listings, as appropriate.

No inferential statistics will be generated.

7.2.1. **Summaries of Numeric Laboratory Results**

Descriptive statistics (n, mean, SD, median, Q1, Q3, minimum, and maximum) will be provided by treatment group for ALT, AST, total bilirubin, alkaline phosphatase, white blood cell (WBC) counts, neutrophils, lymphocytes, hemoglobin, platelets, reticulocytes, and international normalized ratio (INR) as follows:

- Baseline values
- Values at each postbaseline visit for hemoglobin and platelets, and at EOT and FU4 for other analytes specified above
- Change from baseline at each postbaseline visit for hemoglobin and platelets, and at EOT and FU4 for other analytes specified above

A baseline laboratory value will be defined as the final assessment performed on or prior to the date/time of first dose of study drug. Change from baseline to a postbaseline visit will be defined as the visit value minus the baseline value. The mean, median, Q1, Q3, minimum, and maximum will be displayed to reported number of digits, SD to reported number of digits plus 1.

Median (Q1, Q3) of the observed values for hemoglobin and platelets will be plotted using a line plot by treatment group and visit.

In the case of multiple values in an analysis window, data will be selected for analysis as described in Section 3.8.3 (Selection of Data in the Event of Multiple Records in a Window).

The number of subjects with hemoglobin < 10 g/dL and < 8.5 g/dL at any postbaseline visits (up to 30 days after the last dose of any study drug) will be summarized by treatment group.

7.2.2. **Graded Laboratory Values**

The Gilead Grading Scale for Severity of Adverse Events and Laboratory Abnormalities will be used for assigning toxicity grades to laboratory results for analysis as Grade 0, Grade 1 (mild), Grade 2 (moderate), Grade 3 (severe), or Grade 4 (potentially life threatening). Grade 0 includes all values that do not meet criteria for an abnormality of at least Grade 1. Some laboratory tests have laboratory toxicity criteria for both increased and decreased levels; analyses for each direction (ie, increased, decreased) will be presented separately.

7.2.2.1. **Treatment-Emergent Laboratory Abnormalities**

Treatment-emergent laboratory abnormalities are defined as values that increase at least 1 toxicity grade from baseline at any postbaseline time point, up to and including the date of last dose of study drug plus 30 days for subjects who permanently discontinued study drug.

If the relevant baseline laboratory value is missing, then any abnormality of at least Grade 1 will be considered treatment emergent.

7.2.2.2. **Summaries of Laboratory Abnormalities**

Laboratory data that are categorical will be summarized using the number and percentage of subjects in the study with the given response at baseline and each scheduled postbaseline visit.

The following summaries (number and percentage of subjects) for treatment-emergent laboratory abnormalities will be provided by analyte and treatment group; subjects will be categorized according to the most severe postbaseline abnormality grade for a given analyte:

- Graded laboratory abnormalities
- Grade 3 or above laboratory abnormalities

For all summaries of laboratory abnormalities, the denominator is the number of subjects with nonmissing postbaseline values up to 30 days after last dose of study drug for the laboratory parameter of interest.

A by-subject listing of treatment-emergent Grade 3 or above laboratory abnormalities will be provided by subject ID number and visit in chronological order. This listing will include all test results that were collected throughout the study for the analyte of interest, with all applicable severity grades or abnormal flags displayed.

7.3. **Body Weight, Height, and Vital Signs**

Vital signs (systolic and diastolic blood pressure [mmHg], pulse [beats/min]) at each visit, and change from baseline at each visit will be summarized for the Safety Analysis Set using descriptive statistics (n, mean, SD, median, Q1, Q3, minimum, and maximum) by treatment group. The baseline value will be defined as the last available value collected on or prior to the date/time of first dose of study drug. Change from baseline to a postbaseline visit will be defined as the postbaseline value minus the baseline value.

In the case of multiple values in an analysis window, data will be selected for analysis as described in Section 3.8.3 (Selection of Data in the Event of Multiple Records in a Window). No inferential statistics will be generated.

A by-subject listing of vital signs (systolic and diastolic blood pressure [mmHg], pulse [beats/min], respiration [breaths/min], and body temperature [°C]) will be provided by subject ID number and visit in chronological order. In the same manner, a by-subject listing of body weight, height, and BMI will be provided separately.

7.4. **Prior and Concomitant Medications**

Medications collected at Screening and during the study will be coded using the current version of the World Health Organization (WHO) Drug dictionary. The medications will be categorized as prior, concomitant, or both using the following definitions:

- Prior medications: any medications taken prior to the initial study drug dosing date
- Concomitant medications: any medications initially taken on or after the initial study drug dosing date and within the study drug's treatment period (including study drug's therapeutic reach).
- Prior and concomitant medications: any medications taken both prior to and on or after the initial study drug dosing date and within the study drug's treatment period (including study drug's therapeutic reach); or any medications taken prior to the Baseline visit date with a stop date of "continuing"

Concomitant medications will be summarized by Anatomical Therapeutic Chemical (ATC) drug class Level 2, and preferred name using the number and percentage of subjects for each treatment group. A subject reporting the same medication more than once will be counted only once when calculating the number and percentage of subjects who received that medication. The summary of concomitant medications will be ordered by descending active treatment group frequency of ATC drug classes and then preferred names within an ATC medical class. For drugs with the same frequency, sorting will be done alphabetically.

Summaries will be based on the Safety Analysis Set. No inferential statistics will be generated.

For purposes of analysis, any medication with a stop date that is on or prior to the initial study drug dosing date or start date that is after the last study drug dosing date will be excluded from a concomitant medication summary. If a partial stop date is entered, any medication with the month and year (if day is missing) or year (if day and month are missing) prior to the initial study drug dosing date will be excluded from the concomitant medication summary. If a partial start date is entered, then any medication with the month and year (if day is missing) or year (if day and month are missing) after the study drug stop date will be excluded from the concomitant medication summary. Medications with completely missing dates will be included in the concomitant medication summary.

All prior and concomitant medications (other than per-protocol study drugs) will be provided in a by-subject listing sorted by subject ID number and administration date in chronological order.

